PROTOCOL COVER SHEET

Immediate Weight-bearing Verses Non-Weight-bearing after Foot & Ankle Surgery: A Prospective Analysis

04/29/2019

PRINCIPAL INVESTIGATOR [name], DPM, FACFAS

CO-INVESTIGATORS [name], DPM [name], DPM, FACFAS THE FOOT & ANKLE INSTITUTE STEEL VALLEY ORTHOPAEDIC AND SPORTS MEDICINE [name] [contact]

Email: [contact]

ABBREVIATIONS AND DEFINITIONS OF TERMS

NWB	Non-weight-bearing
WB	Weight-bearing
AE	Adverse event
SAE	Serious adverse event

ABSTRACT

In recent years, significant attention has been placed on the safety and efficacy of immediate weight-bearing following foot and ankle surgery. Returning patients to their previous activities as quickly as possible following surgery is always in the mind of providers, but the question of when has been difficult to answer.

Objectives:

The primary objective is to assess if immediate weight-bearing following foot and ankle surgery will yield equivalent, if not superior outcomes to the traditional non-weight-bearing post-operative course, while avoiding the undesirable effects commonly experienced during extended periods of non-weight-bearing. This will be determined by serial radiographs and/or other appropriate imaging modalities, physical exams and using patient self-reported pre- and post-operative SF-36 and AOFAS questionnaires.

Study Design:

Prospective, randomized controlled trial.

Setting/Participants:

Patients will be consented from 5 sites West Penn Hospital, Jefferson Regional Hospital, Forbes Regional Hospital, Bethel Park Surgery Center, and Monroeville Surgery Center and the level of care will include both inpatient and outpatient.

The subjects will be identified/recruited during clinic hours as patients requiring an elective or traumatic foot and ankle surgery. During the clinic hours the primary investigator and/or the co-investigator will obtain full consent from the patient. We will recruit a minimum of 115 participants into each of two study arms, an immediate weight-bearing arm and a non-weight-bearing arm, so 230 participants will be included. Patients will be eligible if they are undergoing elective or traumatic foot and ankle surgery. Exclusion criteria will include any patient less than 18 years of age & over 89, history of foot or ankle surgery on the surgical limb, any degree of diagnosed peripheral neuropathy or peripheral vascular disease, infection, and/or unwillingness to participate at random in one of the two study arms.

Study Interventions and Measures:

We will be assessing the difference in two groups; immediate protected weight-bearing in a CAM walking boot vs strict non-weight-bearing for 6 weeks following foot and ankle surgery. Monitoring will be done by way of clinical follow-up, serial radiographs and/or other appropriate imaging modalities, and patient reported outcomes by way of AOFAS and SF-36 surveys.

Surgical procedures performed on patients included in the study will vary, as will the outcome measures for each procedure. Osseous fusions, including both elective joint fusions and bone healing following trauma, will be assessed by both clinical and radiographic evaluation. Soft tissue procedures, including elective stabilization and traumatic soft tissue repairs, will be assessed clinically and with imaging modalities

deemed appropriate. Complications during the perioperative and post-operative periods, such as non-union, infection, etc. will be included in the outcomes. All participants will also complete AOFAS and SF-36 surveys in the pre-operative and post-operative periods. We will also include return to work, activity, sport, etc. where appropriate.

Study Phase	Screening	Surgery	Post-op 2-3 w	Post-op 6-8 w	Post-op 3 m	Post-op 6 m	Post-op 1 yr	Post-op 2 yr	Unscheduled Visits
Visit Number	1		2	3	4	5	6	7	
Informed									
Informed Consent/Assent	x								
Review Inclusion/Exclusion									
Criteria	х								
Randomization	x								
Demographics/PMH	x								
Physical Examination	x		x	x	x	x	x	x	x
Adverse Event Assessment			x	x	x	x	x	x	x
Radiographs/Imagining	х		x	x	x	x	x	x	x
Complete AOFAS/SF- 36 survey	x			x	x		x	x	

Table 1: Schedule of Study Procedures

1 BACKGROUND INFORMATION AND RATIONALE

1.1 Introduction

There is an ongoing debate within the surgical community as to whether it is best to keep patients who have undergone foot and ankle surgery non-weight-bearing (NWB) for an extended period of time versus allowing them to bear weight early, or on occasion, immediately. The standard for many foot and ankle procedures involving fusion of bone and repair of ligaments and tendons has been to keep the patient completely NWB for 6-8 weeks, or the approximate time it takes for bone and tendon to heal, on average. This standard has been challenged in recent years, with more surgeons allowing their patients to bear weight earlier than previously considered safe. Our aim is to assess if immediate weightbearing following any foot and ankle procedure is equally as safe and effective as an extended course of NWB in patients meeting our inclusion criteria.

1.2 Relevant Literature and Data

The available literature has included a number of different procedures where immediate or early weight-bearing has been allowed. In regards to 1st metatarsal-phalangeal joint fusions, Dayton and McCall reported immediate weight-bearing postoperatively in 42 patients with 47 fusions fixated with 2 crossed screws (n=30), 1 screw and 1 k-wire (n=12), and 2 or more k-wires (n=5). Postoperative evaluation was performed at weeks 1, 2, 4, 6, 9, and 12. The overall union rate was 100%, with an average return to athletic shoes at 6.24 weeks. (1) Mah and Banks described a fixation method a 3 crossing k-wires with immediate weight-bearing in a modified post-op shoe with hallux cutout to restrict loading of the hallux. Twenty-two consecutive cases in 20 patients were retrospectively reviewed. Standard AP and lateral radiographs were used to monitor bone healing, with the pins being removed at 6 weeks and the post-op shoe employed for 8 weeks. Solid fusion was observed in 19 patients (86.36%) between 6-8 weeks postoperative. Two feet (9.1%) had nonunion and 1 foot (4.55%) had a delayed union. (2)

There is also extensive evidence that midfoot fusions such as the Lapidus procedure have had good results following immediate or early weight-bearing. Blitz et al. were able to challenge the traditional postoperative non-weight-bearing period by using a 2 or 3 crossed screw fixation technique and allowing the patient to protected weight bear after approximately two weeks. Using both a curettage joint prep technique by one surgeon and planar resection by another surgeon, the joints were prepped to bleeding bone and then fixated with two crossing screws using lag technique. A third screw was used across the 1st and 2nd cuneiforms depending on surgeon judgment for adequate fixation. The results of these procedures were reviewed retrospectively. Of the 80 feet in which the results were reviewed, protected weight-bearing began at a mean of 14.8 days postop, with 100% going on to successful union at a mean time of 44.5 days. (3) Basile et al. investigated the outcomes of patients undergoing Lapidus who were allowed immediate weight-bearing in a removable boot with those made non-weight-bearing in a short leg cast for 6 weeks. They assessed first intermetatarsal angle and first ray elevation measurement radiographically immediately postoperative and then at the 6-month postoperative visit. In a total of 41 feet, there were no significant radiographic changes between the two groups in regards to radiographic evaluation and no non-unions or mal-unions were observed in either group. (4) Using a plantar oriented plate for Lapidus fixation, Gutteck et al. analyzed results between restricted weight-bearing with floor contact (NWB) and immediate full weight-bearing (FWB), both in short arthrodesis shoes. They reviewed 17 cases in each group and found there was no statistically significant difference in radiographic results, AOFAS scores or visual analog scale scores. They did, however, show there was a significant difference in time to return to work, as the FWB group was fit to return to work at a mean of 30.8 days postoperatively, while the NWB group averaged 57 days. (5)

There is also substantial evidence early or immediate weight-bearing is an alternative following trauma. Maffulli et al. performed a comparative longitudinal study placing patients undergoing open repair of midsubstance Achilles tendon tears into two groups, an

early weight-bearing and ankle mobilization group versus an immobilization group. The immobilization group was non-weight-bearing and underwent cast changes every 2 weeks for 6 weeks until a plantigrade ankle position was achieved, at which point they were advised to bear weight. The early weight-bearing group was placed in a weight-bearing cast for two weeks and encouraged to bear weight as tolerated. A single cast change was performed at 2 weeks and an anterior splint was applied to control dorsiflexion for the next 4 weeks. Both groups attended physiotherapy postoperatively. Results showed the early weight-bearing group had fewer outpatient visits, discarded their crutches after an average of 2.5 weeks and were more satisfied with their surgery. The non-weight-bearing group discarded their crutches at an average of 5.5 weeks. And while the early weight-bearing group attended an average of 6.1 therapy sessions over 2.1 months, the non-weightbearing group needed an average of 13.6 sessions over an average of 4.6 months. (6) Costa et al performed an additional early study looking at the difference in postoperative outcomes between early weight-bearing and traditional non-weight-bearing. Their randomized controlled trial on operatively treated patients placed patient in one of two groups: one which could immediately weight bear in a carbon-fiber orthosis with three 1.5 cm heel raises (n=23), known as the treatment group, or one which was non-weightbearing in a traditional plaster cast postoperatively (n=25), the control group. Subjects were evaluated every two weeks for eight weeks; with each visit allowing both the plaster group and the heel raise group to progressively return to a plantigrade position from equinus. Results showed significant differences in time to return to walking and return to stair climbing, in favor of the treatment group, though no difference was observed in time to return to sport or work. (7) Suchak et al. evaluated 98 patients divided into two groups, an early-weight-bearing group or a non-weight-bearing group. Weight-bearing status was validated using a pressure sensor in a fixed-hinge ankle-foot orthosis and assessment was performed at six weeks, three months, and six months. Using the RAND 36-Item Health Survey, health-related quality of life was assessed. Results were significantly better for the weight-bearing group in the domains of physical functioning, social functioning, roleemotional, and vitality scores at six weeks. Patients in the weight-bearing group also reported fewer limitations of daily activities. No re-rupture occurred in either group. (8) Huang et al. performed a systematic review with Meta-analysis of the literature between 1990-2013, and found that postoperative early weight-bearing combined with early ankle motion exercises achieves superior and more rapid functional recovery versus conventional immobilization after surgical treatment of Achilles tendon repair. Of note, they found few advantages when only early ankle motion exercises were applied. (9) Valkering and Aufwerber, with their colleagues, looked at the healing process of Achilles tendon ruptures after surgery in a novel way, when they used in vivo microdialysis to examine healing metabolites. In their prospective randomized (controlled trial, they divided patients into two groups, a post-operative functional weight-bearing mobilization group (n=27) and a non-weight-bearing group placed in a plaster cast (n=29). Both groups underwent direct repair of the Achilles tendon rupture, and were then divided into their postoperative groups. The weight-bearing group was allowed to be weight-bearing in a controlled orthosis, allowing 15-30 degrees of plantarflexion. The non-weight-bearing group went into

a plaster cast for 2 weeks, followed by a boot with traditional wedge progression until they reached a plantigrade orientation after 4 additional weeks. In their microdialysis analysis, they found that the healing tendons in both groups exhibited increased levels of metabolites glutamate, lactate, and pyruvate, compared to the subject's contralateral tendon, but the functional weight-bearing group had a significantly higher concentration of glutamate compared to the non-weight-bearing cast group. This correlated to improved functional outcomes at 6 months, and supported their conclusion that functional weight-bearing enhances early healing response after Achilles tendon repair. (10)

In the review of the literature, two separate systemic reviews were identified, which support early weight-bearing after ankle fracture repair when compared to late weightbearing or non-weight-bearing for six weeks following surgery. These reviews found no significant adverse results in the early weight-bearing groups, while finding earlier return to previous activities and earlier return to work. (11,12). Additionally, Assal et al. was able to show that, with augmented fixation, early weight-bearing in older patients (greater than 70) with Weber B ankle fractures was a safe and satisfactory method of postoperative care. (13) Starkweather et al. found no malunions or nonunions, and a 9.5% complication rate in patients allowed to be protective weight-bearing following ankle fracture ORIF, while Firoozabadi et al. saw a complication rate of 8% and a loss of correction in only 1 of 26 (4%) patients allowed to immediately bear weight following ankle ORIF. (14, 15) In a randomized control trial, Dehghan et al. divided 110 patients into an early WB group (2 weeks) and a late WB group (6 weeks) and assessed time to return to work, SF-36 scores, and rates of complications. They found no difference in return to work between the two groups, but the early WB group showed significantly improved SF-36 scores on both physical and mental components. Early WB was also found to have similar wound complication rates, with no cases of fixation failure or loss of reduction. The late WB group additionally showed higher rates of hardware removal due to irritation. (19% vs 2%) (16)

In regards to calcaneal fractures, it is commonly understood that three months of nonweight-bearing has been the traditional standard of care following open reduction internal fixation. Both Hyer et al. and Kayali et al. performed retrospective reviews of early weightbearing following open reduction and internal fixation of calcaneal fractures using locking plate fixation, and their results were significant for no unfavorable effects of early weightbearing. (17, 18) Park et al. retrospectively reviewed 86 patients with acute fifth metatarsal base fractures, divided into conservatively treated versus operatively treated and then further grouped into early weight-bearing or late. They analyzed bone resorption, clinical union, and AOFAS and VAS scores, with results showing no differences in AOFAS or VAS scores, fewer cases of bone resorption in the early weight-bearing groups and earlier bony unions in the early weight-bearing groups. Their conclusion was early weight-bearing may help this population, regardless of surgical or conservative treatment. (19) Wagner et al. retrospectively reviewed 22 patients who suffered low-energy Lisfranc injuries who were then subsequently treated with percutaneous screw fixation and early weight-bearing during the third postoperative week. Findings were significant for a complete satisfaction rate of 90.9%, an average AOFAS score of 94, and an average return to work of 7 weeks with return to symptom-free sport activities at 12.4 weeks. (20)

1.3 Compliance Statement

This study will be conducted in full accordance all applicable Allegheny Health Network Research Policies and Procedures and all applicable Federal and state laws and regulations including 45 CFR 46. All episodes of noncompliance will be documented. The investigators will perform the study in accordance with this protocol, will obtain consent and will report unanticipated problems involving risks to subjects or others in accordance with The ASRI-WPAHS IRB Policies and Procedures and all federal requirements. Collection, recording, and reporting of data will be accurate and will ensure the privacy, health, and welfare of research subjects during and after the study.

2 STUDY OBJECTIVES

The purpose of the study is to determine the safety and efficacy of immediate weightbearing following foot and ankle surgery compared to the traditional non-weight-bearing post-operative course.

2.1 Primary Objective (or Aim)

The primary objective of this study is to determine whether immediate weight-bearing following foot and ankle surgery provides similar or superior results to the traditional non-weight-bearing post-operative course, while reducing the disuse atrophy and length of rehabilitation necessary to recover during the transition to weight-bearing following an extended course of non-weight-bearing. This will be done by way of clinical follow-up, serial radiographs and/or other appropriate imaging modalities, and patient reported outcomes by way of AOFAS and SF-36 surveys.

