6 STATISTICAL CONSIDERATIONS

The purpose of the study is to compare the results of immediate weight-bearing versus non-weight-bearing after foot and ankle surgery.

It is hypothesized that immediate weight-bearing following foot and ankle surgery would provide better patient satisfaction with functional outcomes compared to non-weight-bearing after foot and ankle surgery.

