6.4 Statistical Methods

6.4.1 Analysis of Primary Outcome of Interest

All analysis will begin with assessment of the normality of continuous variables using the Kolmogorov-Smirnov test. Normally distributed continuous variables will be reported as means and standard deviations; non-normally distributed data as median and interguartile range. Categorical data will be reported as counts and percentages. The Student's t-test will be used to compare continuous demographic and clinical data between the immediate weight-bearing and non-weight-bearing groups. The chi-square test or Fisher's exact test will be used to compare categorical data between groups. Cronbach's alpha will be used to measure reliability, or internal consistency, of both the Medical Outcomes Study 36-Item Short Form Health Survey (SF-36) and the AOFAS Ankle-Hindfoot Scale survey (AOFAS). Spearman's rank correlation coefficient will be used to assess the relationship between the physical and mental component scores and the eight subdomain scores from the SF-36 and the pain, function and alignment scores of the AOFAS. SF-36 scores and AOFAS scores will be adjusted for patient age, gender, BMI and presence of diabetes mellitus. Nonparametric tests will be used when data breaks the normality assumption. A value of p<.05 on twotailed testing will be considered statistically significant. Statistical analysis will be performed using IBM-SPSS Statistics, version 24.0 (IBM-SPSS Inc., Armonk, NY). Using one-way repeated measures analysis of variance (ANOVA), differences over time in radiographic and advanced imaging parameters will be assessed separately for the immediate weight-bearing and non-weight-bearing groups. Two-way repeated measures ANOVA will be used to assess differences over time in these parameters between the two groups. Tukey's test or Dunn's procedure will be used for post-hoc pairwise comparisons, as indicated.

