Descriptive statistics on the physical and mental component scores and the eight subdomain scores from the SF-36 will be reported for the immediate weight-bearing and non-weight bearing groups. In order to examine differences in SF-36 scores within each group over time, a one-way repeated measures ANOVA will be conducted to determine if the SF-36 scores are significantly different between visits (e.g., screening, post-operative at 6-8 weeks, post-operative at 12 months, and post- operative at 24 months). A two-way repeated measures ANOVA will be conducted to determine if the SF-36 scores are significantly be conducted to determine if the SF-36 scores are significantly be conducted to determine if the SF-36 scores are significantly be conducted to determine if the SF-36 scores are significantly be conducted to determine if the SF-36 scores are significantly be conducted to determine if the SF-36 scores are significantly be conducted to determine if the SF-36 scores are significantly be conducted to determine if the SF-36 scores are significantly different between the two groups for these same visits. Post-hoc pairwise comparisons using Tukey's test or Dunn's procedure will be performed, as indicated.

Descriptive statistics on the pain, function and alignment component scores from the AOFAS will be reported for the immediate weight-bearing and non-weight bearing groups. In order to examine differences in AOFAS scores within each group over time, a one-way repeated measures ANOVA will be conducted to determine if the AOFAS scores are significantly different between visits (e.g., screening, post-operative at 6 – 8 weeks, post-operative at 12 months, and post-operative at 24 months). A two-way repeated measures ANOVA will be conducted to determine if the AOFAS scores are significantly different between visits. Post-hoc pairwise comparisons using Tukey's test or Dunn's procedure will be performed, as indicated.

The chi-square test will be used to examine the frequency of complications during the perioperative and post-operative periods, osseous healing as assessed by both clinical and radiographic evaluation and frequency of soft tissue procedures between the immediate weight-bearing and non-weight bearing groups.

Logistic regression analysis will be performed to assess which patient characteristics and surgical characteristics are associated with higher SF-36 scores and AOFAS scores.

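### The primary objective claims similar or superior results, but the statistical section tests only for a difference and gives no rule for concluding similarity

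*Combined protocol and SAP*

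**What the plan says.** Three places state an aim of being no worse than, or the same as, control:

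- Section 2.1, the formal primary objective, asks whether immediate weight-bearing "provides similar or superior results to the traditional non-weight-bearing post-operative course". It counts clinical follow-up, imaging, AOFAS and SF-36 among the results.
- The Abstract (Objectives) asks whether it "will yield equivalent, if not superior outcomes to the traditional non-weight-bearing post-operative course".
- Section 1.1 gives the aim as whether it "is equally as safe and effective as an extended course of NWB in patients meeting our inclusion criteria".

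Section 6 is built for a different question:

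- The hypothesis is that immediate weight-bearing "would provide better patient satisfaction with functional outcomes compared to non-weight-bearing after foot and ankle surgery".
- Section 6.4.1 sets the significance rule: "A value of p<.05 on twotailed testing will be considered statistically significant".
- For SF-36, a two-way repeated measures ANOVA asks whether "SF-36 scores are significantly different between the two groups for these same visits".
- For safety, "The chi-square test will be used to examine the frequency of complications during the perioperative and post-operative periods", and more generally "The chi-square test or Fisher's exact test will be used to compare categorical data between groups".
- Section 6.5 uses a two-sided .05 t-test and 100 evaluable patients per arm, raised to 115 for loss to follow-up. Its 80% power is for detecting d = 0.40.
- Section 7.3.1 plans a look after 10 patients per arm, to see whether complications are clearly higher with immediate weight-bearing. It is a trigger for stopping.

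**The concern.** A test of difference can support superiority. It cannot support similarity, because a non-significant p-value may reflect either a small true difference or an imprecise estimate. To conclude that one arm is no worse, a plan must say in advance how large a loss would be tolerated and what the confidence interval must exclude. This plan does neither.

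If superiority is not shown, the investigators still have a primary objective that allows a favourable conclusion, and no pre-specified way to reach or reject it. The documents do not say that p>.05 will be read as similarity, but they offer no other basis. The same gap affects the safety claim, which matters because section 2 makes safety a purpose of the study and section 7.3.4 accepts a possible small increase in complications.

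**Working it through.** **Inputs.** From section 6.5: 100 evaluable and 115 enrolled per arm, two-sided alpha .05, d = 0.40. Complication rates and between-visit correlations are not in the documents, so the values below are assumptions. Differences are immediate minus non-weight-bearing, in SD units, with higher scores better.

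**1. The plan's own figure.** The noncentral t solution for d = 0.40 and 80% power is 99.08, so 100 per arm. Power at 100 per arm is 80.4%, and 100 + 15 = 115. The sample size is correct, as a calculation for detecting a difference.

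**2. Chance of a non-significant result when immediate weight-bearing is worse** (1 − power, same t-test, 100 per arm).

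| True loss | Non-significant |
|---|---|
| 0.20 SD | 70.9% |
| 0.30 SD | 44.0% |
| 0.40 SD | 19.6% |

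**3. What a non-significant interval leaves open.** Half-width of the 95% CI = t(.975, 198) × √(2/100) = 0.279 SD. A non-significant interval still includes a 0.20 SD loss when the estimate is at or below 0.279 − 0.20 = +0.079 SD. It includes a 0.40 SD loss when the estimate is at or below 0.279 − 0.40 = −0.121 SD. With a normal estimate and SE = √(2/100) = 0.141, the share of non-significant results is:

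| True difference | Includes 0.20 SD loss | Includes 0.40 SD loss |
|---|---|---|
| 0 | 72% | 18% |
| −0.20 SD | 97% | 59% |

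**4. Sensitivity to the planned repeated measures analysis.** Assume equal SDs, one common correlation r between visits, and a constant effect. For the mean of k post-operative visits minus screening, the variance factor relative to a single score is (1 + (k−1)r)/k + 1 − 2r. The case k = 3 uses the three post-operative visits that section 6.4.1 gives as examples.

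| Contrast | r | Factor | Half-width | 0.20 SD loss non-significant |
|---|---|---|---|---|
| k = 3 | 0.3 | 0.933 | 0.269 | 69% |
| k = 3 | 0.5 | 0.667 | 0.228 | 59% |
| k = 3 | 0.7 | 0.400 | 0.176 | 40% |
| k = 1 | 0.3 | 1.400 | 0.330 | 78% |
| k = 1 | 0.5 | 1.000 | 0.279 | 71% |
| k = 1 | 0.7 | 0.600 | 0.216 | 56% |

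**5. Complications** (exact binomial, rates assumed). Probability of p ≥ .05:

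| Rates | Chi-square, 115 per arm | Fisher, 115 per arm | Chi-square, 100 per arm |
|---|---|---|---|
| 5% v 10% | 69% | 79% | 73% |
| 9% v 18% | 48% | 56% | 53% |
| 20% v 30% | 58% | 64% | 63% |

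Section 7.3.1 names no test. If Fisher's test were used at 10 per arm with no events among controls, 4 v 0 gives p = .087 and 5 v 0 gives p = .033. That look cannot establish equal safety.

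**The case against.** The strongest reply is that section 6 is a coherent superiority plan with correct arithmetic, that nothing in it announces p>.05 as similarity, and that the main remedy is a change of wording. On that view, harm arises only if the authors later draw a conclusion that the plan never promised. Moreover, *similar or superior* is an either/or claim, so a significant superiority result would satisfy it, and section 1.1 is background, not the formal objective.

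Part of this stands. The gap opens only when superiority is not shown. But that outcome is one the objective explicitly provides for, and section 2.1, not only the background, contains the wording.

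There are also fair objections to the figures:

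- The headline percentages use the sample-size t-test, not the planned ANOVA. A baseline-adjusted mean of three post-operative visits, with r from 0.3 to 0.7, has variance factor (1 + 2r)/3 − r². Its half-width is 0.19 to 0.16 SD, and it still misses a 0.20 SD loss 44% to 29% of the time. The documents do not specify that contrast.
- The three post-operative visits are examples. Section 4.3 schedules surveys at four.
- Taking 115 per arm for complications assumes that nobody is excluded under section 4.5.1. At 100 per arm the miss rates rise.
- At 10 per arm, 5 v 0 is not the only significant split; 7 v 1 gives p = .020.
- For AOFAS, the two-way ANOVA is described only as comparing visits, so its between-arm test is implied and not stated.

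These points change the size of the problem or add to it. None supplies the missing criterion.

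**Conclusion.** The concern holds and must be fixed. The plan states a primary objective that its analysis can answer only if superiority is shown. The sample size is sound for superiority, and no error is alleged there.

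On the t-test of section 6.5, a 0.20 SD loss would go undetected about 71% of the time. Across the repeated measures contrasts considered, including the baseline-adjusted one, the range is about 29% to 78%, depending on assumed correlations. For complications, a doubling from 5% to 10% would be missed about 69% of the time by chi-square with 115 per arm, at assumed rates. That similarity and equal safety have no decision rule depends on none of these assumptions.

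**What to change.** **Main route.** Make these changes before any comparative data are reviewed. The first such look is the one in section 7.3.1, after 10 patients per arm.

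- Keep superiority as the sole primary hypothesis.
- Remove the wording of similarity, equivalence and equal safety from the Abstract, section 1.1, section 2.1 and any planned conclusions.
- Report between-group AOFAS and SF-36 differences, and risk differences for complications and healing, with 95% CIs.
- State that p>.05 will not be read as similarity or equal safety.

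The cost is wording and reporting, with no extra patients. The sponsor gives up the equivalence claim.

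**Alternative, if the sponsor wants to keep the claim.** Pre-specify and justify a non-inferiority margin. Declare similarity only if the lower limit of the two-sided 95% CI for immediate minus non-weight-bearing lies above minus that margin. Restate power, and say which SF-36 score counts and whether both instruments must meet the margin. The 0.40 SD in section 6.5 was chosen as a difference to detect, so it is not a default margin. Exclusion of patients who withdraw before 12 months (section 4.5.1) also needs attention here, since it can bias towards similarity.

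Power for one score, 100 per arm, true difference 0 (non-inferiority at one-sided .025; equivalence by two one-sided tests):

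| Margin | Non-inferiority power | Per arm for 80% | Equivalence, each test .05 | Equivalence, each test .025 |
|---|---|---|---|---|
| 0.20 SD | 29% | 394 | – | – |
| 0.30 SD | 56% | 176 | 36% | 12% |
| 0.40 SD | 80% | 100 | 76% | 61% |

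A one-sided margin supports *similar or superior* only; a claim of equivalence needs the two one-sided tests. A margin on the scores says nothing about safety, so the equal-safety wording should go under either route unless complications get their own justified margin.
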